2.6.11. Relationship of Adverse Events to Study Drug

For each adverse event, its relationship to study drug is determined by investigator and recorded on the eCRF. An adverse event is considered as related to study drug if the relationship is possible or probable.

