Adverse Event Associated With the Use of the Drug

An adverse event is considered associated with the use of the drug if the attribution is possible, probable, or very likely by the definitions listed in Section 12.4.2.

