12.4.2. Attribution Definitions

Not Related

An adverse event that is not related to the use of the drug.

Doubtful

An adverse event for which an alternative explanation is more likely, eg, concomitant drug(s), concomitant disease(s), or the relationship in time suggests that a causal relationship is unlikely.

Possible

An adverse event that might be due to the use of the drug. An alternative explanation, eg, concomitant drug(s), concomitant disease(s), is inconclusive. The relationship in time is reasonable; therefore, the causal relationship cannot be excluded.

Probable

An adverse event that might be due to the use of the drug. The relationship in time is suggestive (eg, confirmed by dechallenge). An alternative explanation is less likely, eg, concomitant drug(s), concomitant disease(s).

Very Likely

An adverse event that is listed as a possible adverse reaction and cannot be reasonably explained by an alternative explanation, eg, concomitant drug(s), concomitant disease(s). The relationship in time is very suggestive (eg, it is confirmed by dechallenge and rechallenge).

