12.6.1. All Adverse Events

The investigator must report all directly observed AEs and all AEs reported by the subject, whether spontaneously or in response to general, nondirected questioning (eg, "How has your health been since the last visit?"). For each AE reported by the subject, the investigator should obtain all the information required to complete the AE page of the eCRF, in accordance with the guidelines that accompany it.

All adverse events and special reporting situations, whether serious or non-serious, will be reported from the time a signed and dated ICF is obtained until 30 days after the last dose of any component of the treatment regimen. As of Amendment 7, only SAEs will be collected (see Table 3 and Attachment 8). Nonserious medical events (signs, symptoms, diagnosis) that occur between the Screening Visit or before the first infusion and the first study drug treatment at Cycle 1 Visit 1 should be documented in the medical history. All AEs that occur in subjects during the AE reporting period must be reported, whether or not the event is treatment related.

Serious adverse events, including those spontaneously reported to the investigator within 30 days of the last dose of any component of the treatment regimen, must be reported using the Serious Adverse Event Form. The sponsor will evaluate any safety information that is spontaneously reported by an investigator beyond the time frame specified in the protocol.

All adverse events, regardless of seriousness, severity, or presumed relationship to study drug, must be recorded using medical terminology in the source document and the CRF. Whenever possible, diagnoses should be given when signs and symptoms are due to a common etiology (eg, cough, runny nose, sneezing, sore throat, and head congestion should be reported as "upper respiratory infection"). Investigators must record in the CRF their opinion concerning the relationship of the adverse event to study therapy. All measures required for adverse event management must be recorded in the source document and reported according to sponsor instructions.

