2.6.12. Treatment Emergent Adverse Events

Treatment emergent adverse events (TEAEs) are defined as any AE with onset date and time on or after that of the first dose of study drug infusion through 30 days after the last dose of study drug or the day prior to start of subsequent therapy, whichever is earlier; or any AE that is considered related to (probably, or possibly related) study drug regardless of the start date of the event. AEs with missing or partial onset date and time will be considered as treatment-emergent unless the onset date and time of an AE can be determined as earlier than that of the first dose, or later than 30 days after last infusion .

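### The SAP's rule for a drug-related adverse event leaves out the protocol's strongest causality rating, 'very likely'

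*SAP*

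**What the plan says.** Protocol 12.4.2 sets out five attribution levels: not related, doubtful, possible, probable and very likely. The last is the strongest: "An adverse event that is listed as a possible adverse reaction and cannot be reasonably explained by an alternative explanation", with timing that points strongly to the drug. Protocol 12.4.1 then draws the line: "An adverse event is considered associated with the use of the drug if the attribution is possible, probable, or very likely". The rating is the investigator's, under Protocol 12.6.1: "Investigators must record in the CRF their opinion concerning the relationship of the adverse event to study therapy".

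The SAP draws the line elsewhere. Section 2.6.11 says: "An adverse event is considered as related to study drug if the relationship is possible or probable". Section 2.6.12 defines a TEAE by two routes. The first is an onset window that ignores attribution: "on or after that of the first dose of study drug infusion through 30 days after the last dose of study drug", closing sooner if another therapy begins ("or the day prior to start of subsequent therapy, whichever is earlier"). The second route admits "any AE that is considered related to (probably, or possibly related) study drug regardless of the start date of the event".

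No SAP section adds *very likely* to the related categories or maps it to *probable*.

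**The concern.** The two documents disagree on which events count as drug-related, and the SAP omits the category in which the investigator is most certain. Because *very likely* sits above *probable*, any cut-off on this scale that admits *probable* should admit it too. The SAP's rule is therefore not a stricter threshold; it removes the top of the scale and keeps the middle.

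The primary objective is the safety profile and the primary endpoint is the incidence of adverse events. SAP section 3 adds that the data cut is meant to support a BLA submission. SAP 6.1.1 splits eight summaries by relationship:

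- all TEAEs
- serious TEAEs
- grade 3 or 4 TEAEs
- TEAEs leading to infusion interruption
- TEAEs leading to prolonged infusion
- treatment discontinuation
- study discontinuation
- death

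If *very likely* events fall on the unrelated side, each of these understates drug-related toxicity.

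There is also a reconciliation problem. Protocol 12.6.1 and 16.2.2 base the reporting of serious unlisted events to investigators and ethics committees on association with the study drug, for which 12.4.1 uses three levels. Related counts derived under the SAP's two levels could disagree with those reports for the same events.

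**Working it through.** The plan gives no figure to reproduce, so the check is logical. Each protocol level is put through three rules: the protocol's (12.4.1), the SAP's (2.6.11) and the relatedness route into the TEAE set (SAP 2.6.12).

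| Attribution level (Protocol 12.4.2) | Drug-associated, Protocol 12.4.1 | Related, SAP 2.6.11 | Admitted by relatedness route, SAP 2.6.12 |
|---|---|---|---|
| Not related | No | No | No |
| Doubtful | No | No | No |
| Possible | Yes | Yes | Yes |
| Probable | Yes | Yes | Yes |
| Very likely | **Yes** | **No** | **No** |

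The protocol counts 3 of 5 levels and the SAP 2 of 5. The only mismatch is the top level, and it appears in both SAP rules.

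**Effect on TEAE status.** For an event rated *very likely*:

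- Onset inside the window: it is a TEAE, since the first route does not look at attribution.
- Onset missing or partial, and not demonstrably outside the window: it is a TEAE by default under SAP 2.6.12.
- Onset before first dose, after subsequent therapy has begun, or more than 30 days after the last dose: it is not a TEAE, although a *possible* or *probable* event with the same date would be.

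The third case can arise. Protocol 12.6 requires second primary malignancies to be reported for 3 years after the last lenalidomide dose. It should be uncommon, because Protocol 12.6.1 ends routine collection 30 days after the last dose of any component.

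**Size in the tables by relationship.** For a given preferred term,

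understatement of related incidence = (subjects whose only drug-related record for that term is rated *very likely*) / N.

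In Phase 2, N is about 30:

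- 1 subject: 1/30 = 3.3 percentage points
- 3 subjects: 3/30 = 10 points
- 6 subjects: 6/30 = 20 points
- 9 subjects: 9/30 = 30 points

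The subject counts are assumed, to show scale. The documents give no distribution of ratings.

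**The case against.** The strongest counter-argument is that the eCRF is not among the documents. SAP 2.6.11 refers to the relationship as recorded there. If the form has no *very likely* option, or if programming merges it into *probable*, no event is misclassified. The amendment history gives some reason for doubt: Amendment 5 moved the adverse event section to a new sponsor's template after the study had started, and the SAP's use of the same two levels twice would fit a different form. This stands as a condition on the practical effect. It does not remove the conflict, because the protocol's scale is the only one documented and no mapping is written down.

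Other points limit the reach of the concern:

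- The primary endpoint is the incidence of all adverse events, not of related ones. In-window totals, including the tables by organ class and by worst grade, are unaffected. This stands.
- SAP 6.1.1 does not say that its tables by relationship have only two categories. If every level were shown separately, *very likely* events would remain visible. That is possible, but nothing specifies it, and 2.6.11 supplies a two-way rule.
- Infusion-related reactions have their own analysis in SAP 6.1.2.1, identified by clinical review, so their overall incidence is not hidden. The tables of interruptions and prolonged infusions by relationship remain exposed. Pausing and restarting an infusion may resemble the dechallenge and rechallenge mentioned under *very likely*, but how investigators would rate such events is an inference.
- No decision rule depends on the SAP definition. There is no formal test, dose-limiting toxicities follow Protocol 6.5, and the Phase 2 dose has already been chosen. This bears on how serious the matter is, not on whether the rule is wrong.

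**Conclusion.** The concern holds. As written, SAP 2.6.11 and 2.6.12 contradict Protocol 12.4.1 by leaving the highest causality rating out of the drug-related events. If the eCRF carries the protocol's five levels and the SAP is programmed literally, every event rated *very likely* is classed as unrelated, and the bias always favours the regimen. The harm lies mainly in the summaries by relationship. Loss from the TEAE set is real but confined to events outside the onset window, so overall TEAE incidence should change little. Each affected Phase 2 subject shifts a related incidence by about 3.3 points; the total shift cannot be worked out from the documents. The correction should be made before the safety tables are produced, because drug-relatedness is a main reading of a study whose primary objective is safety.

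**What to change.** In SAP 2.6.11, define related as possible, probable or very likely. Make the same addition to the parenthesis in SAP 2.6.12. Both then agree with Protocol 12.4.1.

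Before finalising, confirm the attribution options on the eCRF and state in the SAP how each maps to the protocol's five levels. If the form has no *very likely* option, say so, so that the difference from the protocol is explained.

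The cost is two short wording changes, one mapping sentence and one line of derivation code. Some related-event rates may come out slightly less favourable.

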2.6.12. Treatment Emergent Adverse Events

Treatment emergent adverse events (TEAEs) are defined as any AE with onset date and time on or after that of the first dose of study drug infusion through 30 days after the last dose of study drug or the day prior to start of subsequent therapy, whichever is earlier; or any AE that is considered related to (probably, or possibly related) study drug regardless of the start date of the event. AEs with missing or partial onset date and time will be considered as treatment-emergent unless the onset date and time of an AE can be determined as earlier than that of the first dose, or later than 30 days after last infusion .

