For Phase 1 and Phase 2, dexamethasone will be administered at a total dose of 40 mg/week (except for the first week of daratumumab dosing; see below). On the day of the predose infusion of daratumumab (Cycle 1 Visit 1), dexamethasone will be administered at a dose of 20 mg IV before the infusion; no dose will be administered after the infusion. During daratumumab infusion weeks, dexamethasone will be administered on the day of daratumumab infusion as 20 mg IV before the infusion and 20 mg PO the day after the infusion. An equivalent dose may be given in accordance with local standards (Attachment 4). During weeks when no daratumumab infusion is planned, dexamethasone will be administered at a dose of 40 mg/week PO. For both Phase 1 and Phase 2, after the completion of Cycle 6, the administration of dexamethasone may be adjusted at the discretion of the investigator; however, dexamethasone should always be administered at a dose of 20 mg IV on daratumumab infusion days. Dexamethasone will be administered until the subject experiences disease progression or unacceptable toxicity, whichever comes first.

At Cycle 1 Visit 2 (the first full-dose infusion of daratumumab), the subject may either remain hospitalized overnight and be released on the following day or may receive outpatient IV administration at the investigator's discretion. This hospitalization should not be reported as an SAE. Hospitalization is not required for the predose infusion (Cycle 1 Visit 1) because no infusion-related SAEs have been observed during or after the predose infusion of 23 subjects during the GEN501 study.

All subsequent infusions will be performed as outpatient visits. If the subject has not experienced a significant medical event but is hospitalized overnight only for observation, the hospitalization should not be reported as an SAE.

Adverse events will be monitored closely during treatment. Escalation to a new dose level can only be done after evaluation of the safety profile of the previous dose level by the IDMC. After this evaluation, the IDMC will make a recommendation regarding dose escalation.

If the subject must stop either daratumumab, lenalidomide, or dexamethasone, the subject may continue the other components until progression or commencing a new regimen for the treatment of multiple myeloma. However, subjects will still receive dexamethasone as premedication to daratumumab.

9.1.3.1. Treatment Follow-up as per Amendment 8

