1. INTRODUCTION

This is an open-label, dose-escalation, multicenter, Phase 1/2 safety study of daratumumab in combination with lenalidomide and dexamethasone (Len/Dex) in the treatment of subjects with relapsed or relapsed and refractory multiple myeloma. The dose escalation portion of the study (Phase 1) will be a standard 3 + 3 design and will evaluate daratumumab, at doses from 2 mg/kg up to a maximum of 16 mg/kg, in combination with Len/Dex in 28-day treatment cycles. A recommended Phase 2 dose (RP2D) will be determined during Phase 1. The Phase 2 will open to further explore the safety and efficacy of the RP2D in approximately 30 subjects.

This document serves as the statistical analysis plan for the primary analysis, covering both Phase 1 and Phase 2 of the study. As of Amendment 7, the primary analysis will be achieved. All subjects in the study have either received at least 12 months of study drug or have discontinued. Ongoing subjects may continue treatment with study drug with a limited schedule of assessments. The study treatment of daratumumab, lenalidomide or dexamethasone is referred to as the "study drug" throughout.

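### SAP 2.6.12 ends the treatment-emergent window at one point for fully dated adverse events and at another for partly dated ones

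*SAP*

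**What the plan says.** SAP 2.6.12 holds three rules that bear on when an adverse event stops being treatment-emergent.

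- **Main window.** It runs "through 30 days after the last dose of study drug or the day prior to start of subsequent therapy, whichever is earlier". SAP 1 fixes the term: "The study treatment of daratumumab, lenalidomide or dexamethasone is referred to as the" study drug, so the final dose may be of any of the three agents.
- **Related events.** Also counted is "any AE that is considered related to (probably, or possibly related) study drug regardless of the start date of the event".
- **Missing or partial onset.** The default is inclusion: "AEs with missing or partial onset date and time will be considered as treatment-emergent unless the onset date and time of an AE can" be placed before the first dose, or "later than 30 days after last infusion".

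Under Protocol 9.1.3, when one agent has to be stopped, "the subject may continue the other components until progression" or a new myeloma regimen. Protocol 12.6.1 collects adverse events until 30 days after the final dose of any component. Protocol 9.3 makes the incidence of adverse events the primary endpoint, and SAP 6.1 tabulates only treatment-emergent events unless it says otherwise.

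**The concern.** The window for dated events follows all three agents, while the exclusion for partly dated events follows the infusion only. The infused study treatment is daratumumab. SAP 4.4 uses the same phrase for daratumumab exposure, lenalidomide is oral, and intravenous dexamethasone is given before daratumumab infusions (Protocol 6.3). A subject who stops daratumumab and stays on lenalidomide/dexamethasone is therefore still inside the main window after the partial-date cut-off has passed. The partial-date sentence also omits the subsequent-therapy limit.

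At stake is consistency in the tables that describe the primary endpoint. Whether an event is counted should depend on when it happened, not on whether the site recorded the day. The tables by preferred term and grade (SAP 6.1.1) and by onset time for infections and neutropenia (SAP 6.1.2.2 and 6.1.2.3) all take their events from this definition.

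**Working it through.** The plan states no figure on this point, so there is none to reproduce. The check compares the two rules and then does date arithmetic.

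**Inputs**
- Main end: "through 30 days after the last dose of study drug", or the day before subsequent therapy if earlier (SAP 2.6.12).
- Partial-date end: 30 days after the last infusion (SAP 2.6.12).
- Daratumumab from Cycle 7: Day 1 of each 28-day cycle (Protocol 6.1).
- Lenalidomide: Days 1 to 21 of each 28-day cycle (Protocol 6.2).
- Number of further cycles on lenalidomide after the last infusion, m: not given in the documents. I assume a range of 0 to 3.

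**Formula.** Call the day of the last infusion Day 1.
- Partial-date cut-off = 1 + 30 = Day 31.
- Last lenalidomide day = 28m + 21.
- Main cut-off = 28m + 21 + 30 = 28m + 51.
- Gap = (28m + 51) − 31 = 28m + 20 days.

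| m | Partial-date cut-off | Main cut-off | Gap (days) |
|---|---|---|---|
| 0 | Day 31 | Day 51 | 20 |
| 1 | Day 31 | Day 79 | 48 |
| 2 | Day 31 | Day 107 | 76 |
| 3 | Day 31 | Day 135 | 104 |

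The gap is not zero even at m = 0, because lenalidomide runs on to Day 21 after a Day 1 infusion.

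**Example of exclusion (illustrative dates).** The last infusion is on 1 September 2014, followed by three further lenalidomide cycles. The partial-date cut-off is 1 October 2014. The last lenalidomide dose is 104 days after the infusion, on 14 December 2014, so the main cut-off is 13 January 2015. An event not rated possibly or probably related, recorded only as November 2014, is certainly later than 1 October. It loses the default and can be left out. With any full November date it counts.

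**Example of retention (illustrative dates).** The last infusion is on 15 September 2014 and subsequent therapy starts on 28 September. The main window closes on 27 September. The partial-date cut-off is 15 October. An event recorded only as October 2014 cannot be shown to fall after 15 October, so it is kept. If it is not rated related and is dated in full as 5 October, it is excluded.

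**Which events are exposed.** For exclusion, all of these must hold:
- the onset is partial;
- what is recorded still proves onset after the partial-date cut-off;
- the true onset is inside the main window;
- the event is not rated possibly or probably related.

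A completely missing onset stays treatment-emergent by default, and SAP 2.5.1 imputes it to the first dose date.

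**Rough scale inside the gap (my assumptions).** Take events with month-only onset that are not rated related, with onset uniform from the last infusion to the main cut-off and infusion dates uniform over a year. The literal rule drops about 14% of them at m = 0, 42% at m = 1, 57% at m = 2 and 66% at m = 3. These are shares of a group whose size the documents do not give, so they say nothing about how many events the trial would lose.

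**The case against.** The strongest reply has four parts.

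**Related events are protected.** A partly dated event rated possibly or probably related to any of the three agents stays in, whatever its date. This stands. A reader might infer that the rule undercounts the toxicity of continued lenalidomide/dexamethasone. The documents do not support that for events so rated; the exposure is mainly among events rated not related or doubtful. One qualification applies. Protocol 12.4.1 counts an event as drug-associated "if the attribution is possible, probable, or very likely by the definitions listed in Section 12.4.2", but SAP 2.6.11 and 2.6.12 name only possible and probable, so read literally the very-likely category has no protection.

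**Imputation may rescue the event.** SAP 2.5.1 sets a missing day to the first of the month (outside the month of first dose). The November example becomes 1 November 2014, which the main window includes. This stands in part: the SAP does not say whether the imputed date or the partial-date sentence governs. Exclusion is therefore one permissible reading rather than the certain outcome, and two programmers could differ.

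**The gap may be short in practice.** A reader might picture half a year of lenalidomide/dexamethasone after daratumumab. No section gives such a duration. The Amendment 7 entry in the protocol's amendment history records the removal of a limit of 2 additional cycles of lenalidomide/dexamethasone alone. That text is superseded, but it is a reason not to assume a long gap for the period this SAP analyses. This stands, and is why m is left as a short assumed range.

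**The endpoint is descriptive.** SAP 1.3 and 5.1.1 plan no formal test, and a late, unrelated, partly dated event would seldom decide whether a subject had any treatment-emergent event. This stands, and it limits the consequence to individual table cells.

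**Conclusion.** The inconsistency is real and lies within one subsection. Dated and partly dated events are held to different end points, and the difference can both exclude and retain events wrongly. Its size is 28m + 20 days of follow-up per affected subject when lenalidomide is the last agent given and no subsequent therapy intervenes. The number of events in that interval is unknown. The effect is probably small, falling mainly on counts by preferred term, grade and onset time.

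A reader might go further and say that events are dropped from the primary endpoint. That is more than the documents show. Event collection is unaffected, related events are kept, the default favours inclusion, and SAP 2.5.1 may restore the event.

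The conclusion assumes that the last infusion means daratumumab and that the partial-date sentence is applied as written. It is a low-priority correction, worth making because it costs almost nothing.

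**What to change.** In the last sentence of SAP 2.6.12, replace the last-infusion cut-off with the end used by the main rule. A partly dated event would then lose the default only if its onset is shown to be more than 30 days past the final dose of any component (daratumumab, lenalidomide or dexamethasone), or on or after the start of subsequent therapy, whichever limit comes first. Add one sentence stating that onset dates imputed under SAP 2.5.1 are classified by this same window, so that precedence is settled. Both parts are needed. Changing only the drug reference would still let partly dated events after the start of subsequent therapy be kept when dated ones are excluded.

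With one end point in both places the gap is 0 days. The cost is a short text change and the matching line in the derivation of the treatment-emergent flag. No new data are needed, and sample size and trial conduct do not change.
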